5.2.1 Treatment-emergent Adverse Event

An AE is a treatment-emergent AE (TEAE) if the AE start date is

- On or after the date of the first dose of IP and no later than 28 days after the last dose of IP for subjects who have completed study treatment or have discontinued early by the time of database cut, or
- On or after the date of the first dose of IP for subjects who are ongoing with study treatment at the time of database cut.

If the treatment-emergent status of an AE is unclear due to a missing/incomplete start date, it will always be considered treatment-emergent, unless shown otherwise by data. Date imputation rules for missing AE start dates are described in [section 8.3.2](#).

Adverse event started more than 28 days after the last dose of IP will not be considered as a treatment-emergent AE.

5.2.2 Treatment-emergent Adverse Event Leading to Drug Withdrawal, Drug Interruption, or Death, and Drug-related Treatment-emergent Adverse Event

A TEAE leading to drug withdrawal is a TEAE for which the investigator indicates that the action taken with respect to IP is withdrawn permanently. A TEAE leading to drug interruption is a TEAE for which the investigator indicates that the action taken with respect to IP is interrupted. A TEAE leading to death is a TEAE for which the outcome is

fatal. Relationship to IP is based on the investigator's causality judgment; that is, a drug-related AE is an AE indicated by the investigator to have a suspected relationship to IP.

5.2.3 Vital Signs and Weight

Vital signs and weight endpoints include:

- Observed value and change from baseline over time in vital signs (temperature, pulse, and blood pressure)
- Shifts from baseline to post-baseline time points and to the worst post-baseline value in terms of normal/abnormal in pulse and blood pressure (normal ranges are defined as: 60-100 beats/minute for pulse, 90-140 mmHg for systolic blood pressure, and 60-90 mmHg for diastolic blood pressure)
- Observed value, change and percent change from baseline over time in weight

5.2.4 Clinical Laboratory Evaluations

Laboratory evaluations include:

- Observed value and change from baseline over time in hematology and serum chemistry parameters
- Laboratory marked abnormalities and by baseline laboratory category will be analyzed for selected analytes ([Appendix B](#)).
- Shifts from baseline to post-baseline time points and to the worst post-baseline value in terms of normal/abnormal (low or high) in hematology and serum chemistry parameters

5.4 Baseline Definitions

For efficacy analysis and summary of baseline disease characteristics data, baseline is defined as the last value measured prior to or at the randomization date.

For safety analyses in the Placebo-controlled Phase, baseline will be relative to the first dose date following randomization at Week 0. It is the last value measured prior to or on the day of the first dose of IP.

For safety analyses in Apremilast Exposure Period, baseline will be relative to the first apremilast dose date at Week 0 for subjects initially randomized to apremilast or Week 16 for subjects initially randomized to placebo and switched to apremilast in the Extension Phase. It is the last value measured prior to or at the first apremilast dose date.

5.5 Time Points

Time points in all analyses are based on the remapped visits/study weeks using the visit mapping algorithm ([Appendix A](#)), which may or may not be the same as the visits/study weeks as recorded in the database.

6. Analysis Sets

6.1 Intent-to Treat Analysis Set

The intent-to-treat (ITT) analysis set will consist of all subjects who are randomized regardless of whether the subject received IP. Subjects will be included in the treatment group to which they are randomized.

6.1.1 Primary Analysis Set

The primary analysis set is the intent-to-treat analysis set, and will be based on week 16 database.

6.2 Safety Analysis Set

The safety analysis set will consist of all subjects who are randomized and received at least one dose of investigational product (IP). Subjects will be included in the treatment group corresponding to the IP they actually received (apremilast or placebo) for the analyses and summaries using the safety analysis set.

6.3 Per Protocol Set(s)

The per protocol (PP) analysis set will consist of all subjects included in the ITT analysis set who receive at least one dose of IP, have both baseline and at least one post-baseline modified sPGA-G assessment, and have no important protocol deviations which may affect efficacy assessments in the Placebo-controlled Phase.

6.4 Health-related Quality-of-Life or Health Economics Analyses Set(s)

Not applicable.

Not applicable.

6.6 Interim Analyses Set(s)

Not applicable.

6.7 Study-specific Analysis Sets

Not applicable.

7. Planned Analyses

7.1 Interim Analysis and Early Stopping Guidelines

No interim analysis will be conducted.

After all subjects have completed the Week 16 Visit (or discontinued from the study), a Week 16 database restriction will be performed, the primary data analysis will be conducted. However, unblinded data will only be made available to selected Sponsor and Contract Research Organization (CRO) team members involved with analysis of the data and preparation of the regulatory submission activities. All other Sponsor, site, and CRO personnel directly involved with the conduct of the study, will remain blinded to treatment assignments until the final database lock at the conclusion of the study. At the end of the study, after all subjects have completed or have been discontinued from the Apremilast Extension Phase (Weeks 16 to 32) and the Observational Follow-up Phase, the final analysis will be performed, and a final Clinical Study Report will be generated.

7.2 Primary Analysis

The primary analysis will be performed after all subjects have had the opportunity to complete the week 16 visit.

The primary analysis will present data from the completed placebo-controlled phase of the study, including the primary, secondary, and exploratory endpoints, and safety results at week 16. In addition, the primary analysis will present cumulative safety data up to the report's data cutoff date for the active treatment phase, including exposure from both the completed placebo-controlled phase and the ongoing active treatment phase.

7.3 Final Analysis

The final analysis will occur after all subjects have had the opportunity to complete the study (ie, completion of the observational follow-up phase or discontinued the study).

The scope of the final analysis is the evaluation of the remaining efficacy data and final safety data.

7.4 Analysis Phases/Period

For efficacy analysis, different phases will be used; For safety analysis, Placebo-controlled Phase and Apremilast-exposure Period will be used.

7.4.1 Analysis Phases

Per protocol specification, data summary and analysis will be provided for the following phases:

7.4.1.1 Placebo-controlled Phase – Weeks 0 to 16

This phase starts on the day of randomization (Week 0/Visit 2), and stops on either: (1) the day the first IP for the next phase is dispensed at Week 16/Visit 7; or (2) the day of the discontinuation visit if the subject discontinued prior to or at Week 16/Visit 7; or (3) the last known study day if the subject is lost to follow-up prior to Week 16/Visit 7 during the phase.

For safety analysis in subjects who continued treatment in Apremilast Extension Phase (Weeks 16 to 32), the phase stopped one day prior to the first dose date in Apremilast Extension Phase.

For analysis of adverse events, TEAEs in the phase including those with start date at the first IP dose date through either: (1) one day prior to the first IP dose date in Apremilast Extension Phase (Weeks 16 to 32); or (2) 28 days after the last IP dose date for subjects who discontinue after only receiving treatment in the Placebo-controlled Phase.

For safety analysis of visit-based data (ie, laboratory parameters, vital signs, etc), the post-baseline data in the phase including those with assessments dates after the first IP dose date (exclusive) and through either: (1) the first IP dose date (inclusive) in Apremilast Extension Phase (Weeks 16 to 32); or (2) the last visit date within 28 days of the last IP dose date (prior to the first Follow-up Visit) for subjects who discontinue after only receiving treatment in the Placebo-controlled Phase.

At the time of the Week 16 analysis, if the date of the first IP dose date in Apremilast Extension Phase is not available in data base and the subject has not discontinued, the first IP dispensing date will be used instead.

7.4.1.2 Apremilast Extension Phase – Weeks 16 to 32

This phase starts on the day after the first IP is dispensed for the phase at Week 16/Visit 7, and stops on either: (1) the day of Week 32/Visit 10; or (2) the day of the discontinuation visit if the subject discontinued prior to or at Week 32/Visit 10; or (3) the last known study day if the subject is lost to follow-up prior to Week 32/Visit 10 during the phase.

For safety analysis, the phase started at the first dose date in the phase and ended at the last dose date.

For analysis of adverse events, TEAEs in the phase including those starts at the first IP dose date in the phase through 28 days after the last IP dose date for subjects who completed or discontinued treatment in the phase.

For safety analysis of visit-based data (ie, laboratory parameters, vital signs, etc), data in the phase starts at the first IP dose date (exclusive) and stops on the last visit date within 28 days of the last IP dose date (prior to the first Follow-up visit).

7.4.1.3 Observational Follow-up Phase – 4 weeks

Subjects who complete the study or discontinue the study early, will be followed up for 28 days after the last dose of IP.

TEAEs in the Follow-up Phase will include adverse events started after and within 28 days of the last dose date. Those TEAEs will also be summarized in one of the two treatment phases.

7.4.2 Apremilast-exposure Period for Safety Analysis

This period starts on the date of either: (1) the first dose of IP following randomization (Week 0/Visit 2) for subjects who are treated with apremilast from Week 0; or (2) the first dose of IP from the IP dispensed at Week16/Visit 7 for subjects who were originally treated with placebo and are treated with apremilast at Week 16.

This period stops on either: (1) 28 days after the last IP dose date for subjects completed or discontinued treatment from the study; or (2) data cut-off date for ongoing subjects.

7.5 Treatment arms

In general, the treatment arms used in the analyses and summaries in each phase are described below in this section unless otherwise specified.

7.5.1.1 Placebo-controlled Phase (Weeks 0 to 16)

- Placebo
- Apremilast 30 mg BID
- Total (optional, not for the efficacy analysis)

7.5.1.2 Apremilast Extension Phase (Weeks 16 to 32)

Subjects who entered the extension phase will be included in analysis, ie, who were initially randomized to apremilast and continued at Week 16 and who were initially randomized to placebo and switched to apremilast at Week 16.

- Placebo/30 mg BID
- 30 mg BID/30 mg BID

7.5.1.3 Apremilast-exposure Period

Subjects who are treated with at least one dose of apremilast will be included here, which includes all subjects who are randomized to (at Week 0/Visit 2) or switched to (at Week 16/Visit 7) apremilast, and receive at least one dose of apremilast after randomization or Week 16.

- 30 mg BID as Treated

7.5.1.4 Observational Follow-up Phase (4 weeks)

For subjects who entered Follow-up Phase from Placebo-controlled Phase, summaries will be provided by their initial treatment arm:

- Placebo
- 30 mg BID

For subjects who entered Follow-up Phase from Apremilast Extension Phase, summaries will be provided by their treatment sequence:

- Placebo/30 mg BID
- 30 mg BID/30 mg BID

8. Data Screening and Acceptance

8.1 General Principles

The objective of the data screening is to assess the quantity, quality, and statistical characteristics of the data relative to the requirements of the planned analyses.

8.2 Data Handling and Electronic Transfer of Data

The Amgen Global Study Operations-Data Management (GSO-DM) department will provide all data to be used in the planned analyses. This study will use the RAVE database.

8.3 Handling of Missing and Incomplete Data

8.3.1 Efficacy endpoints

Missing data handling methods applied to the analysis for each efficacy endpoints is summarized as below:

Table 1. Summary of missing data handling method applied to the analysis for each efficacy endpoint

Analysis Set [a]	Week	Endpoint	Imputation Method [b]
ITT, PP	0-16	Modified sPGA-G response	MI, NRI, DAO
ITT	0-16	sPGA response	MI, NRI, DAO
ITT	0-16	GPI-NRS response	MI, NRI, DAO
ITT	0-16	BSA change and percent change from baseline	MMRM
ITT	0-16	DLQI change from baseline	MMRM
ITT	0-16	GPSS total score change from baseline	MMRM
ITT	0-16	GPSS individual items scores change from baseline	MMRM
ITT	0-16	DLQI-Q#9 change from baseline	MMRM
ITT (Subjects entered extension phase)	16-32	sPGA-G response, sPGA response, GPI-NRS response	NRI, DAO
ITT (Subjects entered extension phase)	16-32	BSA change and percent change from baseline, DLQI change from baseline, GPSS total score change from baseline, GPSS individual items scores change from baseline, GPI-NRS change from baseline, DLQI-Q#9 change from baseline	DAO

Note: MI = Multiple Imputation; NRI = Non-responder imputation; DAO = Data as Observed; MMRM= Mixed-effect model for repeated measures

[a] See [Section 6](#)
[b] See [Section 9.5](#)

8.3.2 Partially Missing Date Imputation for Adverse Events

Partially missing AE start dates will be imputed in the ADaM dataset for AEs, but partially missing AE end dates will not be imputed in the same dataset. If the AE end date is complete with no missing year, month, or day, and the partially missing start date imputed by the rules below is after the AE end date, then the start date will be imputed by the AE end date.

Subjects who were treated with apremilast at Week 0/Visit 2

The principle of the imputation rules for subjects who were treated with apremilast initially is to treat the AE as treatment-emergent, i.e., occurring on or after the date of the first dose of IP, if possible.

Let an AE start date be represented as " $D_{Event}/M_{Event}/Y_{Event}$ ", and the date of the first dose of IP as " $D_{IP}/M_{IP}/Y_{IP}$ ". The following table gives the imputation rules for partially missing AE start dates for subjects who were treated with apremilast initially.

Table 2. Imputation Rules for Partially Missing AE Start Dates for Subjects Who Were Treated with Apremilast Initially

Scenario	Condition	Imputation Rule
Partially missing date includes year only (both month and day are missing)		
1	$Y_{Event} < Y_{IP}$	12/31/ Y_{Event}
2	Otherwise, i.e., $Y_{IP} \leq Y_{Event}$	Max (date of first dose of IP, 1/1/ Y_{Event})
Partially missing date includes both year and month (only day is missing)		
1	$Y_{Event} < Y_{IP}$, or ($Y_{Event} = Y_{IP}$ and $M_{Event} < M_{IP}$)	Last date of M_{Event}/Y_{Event}
2	Otherwise, i.e., $Y_{IP} < Y_{Event}$, or ($Y_{IP} = Y_{Event}$ and $M_{IP} \leq M_{Event}$)	Max (date of first dose of IP, 1/ M_{Event}/Y_{Event})

Subjects who were treated with placebo at Week 0/Visit 2

The principle of the imputation rules for subjects who were treated with placebo initially and started apremilast treatment at Week 16 is to consider the AE starting on or after the date of the first dose of apremilast, if possible; if the partially missing start date suggests that it is prior to the date of the first dose of apremilast, the AE will be considered starting on or after the date of the first dose of IP, if possible.

The following are 4 scenarios considered in the imputation rules:

1. The partially missing AE start date suggests the date is prior to the date of the first dose of IP: impute it by the latest possible date (determined by the non-missing field of the date);

2. The partially missing AE start date suggests the date is after the date of the first dose of apremilast following Week 16: impute it by the earliest possible date (determined by the non-missing field of the date);
3. The partially missing AE start date is in the same year (if both month and day are missing), or the same year/month (if only day is missing) of the first dose of apremilast following Week 16: impute it by the date of the first dose of apremilast;
4. The partially missing AE start date suggests the date is no earlier than the date of the first dose of IP but prior to the date of the first dose of apremilast following Week 16: impute it by the date of the first dose of IP, or the earliest possible date (determined by the non-missing field of the date), whichever occurs later.

Let an AE start date be represented as " $D_{Event}/M_{Event}/Y_{Event}$ ", the date of the first dose of IP as " $D_{IP}/M_{IP}/Y_{IP}$ ", and the date of the first dose of apremilast following Week 16 as " $D_{APR}/M_{APR}/Y_{APR}$ ". The following table gives the imputation rules for partially missing AE start dates.

Table 3. Imputation Rules for Partially Missing AE Start Dates for Subjects Who Were Treated with Placebo Initially

Scenario	Condition	Imputation Rule
Partially missing date includes year only (both month and day are missing)		
1	$Y_{Event} < Y_{IP}$	12/31/ Y_{Event}
2	$Y_{Event} > Y_{APR}$	1/1/ Y_{Event}
3	$Y_{Event} = Y_{APR}$	Date of first dose of apremilast following Week 16
4	Otherwise, i.e., $Y_{IP} \leq Y_{Event} < Y_{APR}$	Max (date of first dose of IP, 1/1/ Y_{Event})
Partially missing date includes both year and month (only day is missing)		
1	$Y_{Event} < Y_{IP}$, or ($Y_{Event} = Y_{IP}$ and $M_{Event} < M_{IP}$)	Last date of M_{Event}/Y_{Event}
2	$Y_{Event} > Y_{APR}$, or ($Y_{Event} = Y_{APR}$ and $M_{Event} > M_{APR}$)	1/ M_{Event}/Y_{Event}
3	$Y_{Event} = Y_{APR}$ and $M_{Event} = M_{APR}$	Date of first dose of apremilast following Week 16
4	Otherwise, i.e., $Y_{IP} < Y_{Event} < Y_{APR}$, or ($Y_{IP} = Y_{Event} < Y_{APR}$ and $M_{IP} \leq M_{Event}$), or ($Y_{IP} = Y_{Event} = Y_{APR}$ and $M_{IP} \leq M_{Event} < M_{APR}$), or ($Y_{IP} < Y_{Event} = Y_{APR}$ and $M_{Event} < M_{APR}$)	Max (date of first dose of IP, 1/ M_{Event}/Y_{Event})

8.3.3 Prior Concomitant Medications/Procedures

Partially missing start/stop dates for prior/concomitant medications and partially missing start dates for prior/concomitant procedures will be imputed in the ADaM dataset for prior/concomitant medications/procedures. For prior/concomitant medications, if the stop date is complete with no missing year, month, or day, and the partially missing start date imputed by the rule below is after the stop date, then the start date will be imputed by the stop date.

Partially missing prior/concomitant medication/procedure start dates will be imputed by the earliest possible date given the non-missing field(s) of the date.

Partially missing prior/concomitant medication stop dates will be imputed by the latest possible date given the non-missing field(s) of the date.

8.3.4 Medical History

Partially missing medical history start dates will be imputed in the ADaM dataset for medical history (for the purposes of calculating durations of PsA and psoriasis). The 16th of the month will be used to impute a partially missing start date that has only the day missing, and July 1st will be used to impute a partially missing start date that has both the month and day missing.

8.3.5 Treatment Duration

Partially or completely missing last dose dates will be imputed in the ADaM dataset for treatment duration.

When partially missing last dose date is available, set last dose date to the maximum of [the earliest possible date given the non-missing field(s) of last dose date, the minimum of (the latest possible date given the non-missing field(s) of last dose date, last known date in database, first non-missing Early Termination (ET) visit date)]

When last dose date is completely missing, set last dose date to the minimum of (last known date in database, first non-missing Early Termination (ET) visit date)

Last known date in database is defined as maximum of (last visit date, lab, vital signs, AE start or end dates, concomitant medications start or end dates, concomitant procedure date, last dose date from 'Disposition- Treatment' page, treatment exposure start or end dates where doses were completely or partially taken, death date).

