All AEs will be recorded by the investigator from the time the subject signs informed consent until 28 days after the last dose of IP as well as all SAEs made known to the investigator at any time following the protocol-required reporting period or after end of study. All adverse events (serious/non-serious) will be recorded on the CRF, the paper SAE report form (for SAEs) and in the subject's source documents. All SAEs must be reported to Amgen Global Patient Safety within 24 hours of the Investigator's knowledge of the event by recording on the CRF and submitting the SAE information using the paper Serious Adverse Event Report Form by facsimile/email directly to Amgen Global Patient Safety.

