APPENDIX E. TITRATION BLISTER CARD CONFIGURATION

30mg BID Titration and Treatment Card (28 day +5 Extra)

	1	10	20p	30p		1	10p	20p	30p
	2	10	20p	30p		2	10	20p	30p
	3	10	20p	30p		3	10p	20	30p
	4	10p	20	30p		4	10p	20	30p
	5	10p	20	30p		5	10p	20p	30
	6		30			6		30	
	7		30			7		30	
	8		30			8		30	
	9		30			9		30	
	10		30			10		30	
	11		30			11		30	
	12		30			12		30	
	13		30			13		30	
	14		30			14		30	
	15		30			15		30	
	16		30			16		30	
	17		30			17		30	
	18		30			18		30	
	19		30			19		30	
	20		30			20		30	
	21		30			21		30	
	22		30			22		30	
	23		30			23		30	
	24		30			24		30	
	25		30			25		30	
	26		30			26		30	
	27		30			27		30	
	28		30			28		30	
	29		30			29		30	
	30		30			30		30	
	31		30			31		30	
	32		30			32		30	
	33		30			33		30	

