9.6 Safety Analyses

9.6.1 Analyses of Primary Safety Endpoint(s)

Safety will be assessed via descriptive statistics. Unless otherwise specified, all safety analyses described in this section will be performed for both the Placebo-controlled Phase and the Apremilast-exposure Period. The safety analyses for the Placebo-controlled Phase will be based on the safety population and presented by treatment group (placebo arm or apremilast arm), and the safety analyses for the Apremilast-exposure Period will be based on the apremilast subjects as treated population and

presented by treatment group (Placebo/30 mg BID, 30 mg BID as Initiated and 30 mg BID as Treated).

For the analyses of AEs and lab marked abnormalities, the following endpoints will also be summarized:

- Subject incidence: Subject incidence (i.e., percentage [%] used in a frequency summary) is defined as the number of subjects with the specific event divided by the number of subjects included in the analysis. Subjects with multiple occurrences of the specific event in the specific analysis period will be counted only once in the numerator.
- Exposure-adjusted incidence rate (EAIR) per 100 subject-years: The EAIR per 100 subject-years is defined as 100 times the number of subjects with the specific event divided by the total exposure time (in years) among subjects included in the analysis. Subjects with multiple occurrences of the specific event in the specific analysis period will be counted only once in the numerator. The exposure time for a subject without the specific event is the treatment duration, whereas the exposure time for a subject with the specific event is the treatment duration up to the start date (inclusive) of the first occurrence of the specific event. The total exposure time in years is calculated by dividing the sum of exposure time in days over all subjects included in the analysis by 365.25. The EAIR per 100 subject-years is interpreted as the expected number of subjects with at least one occurrence of the specific event per 100 subject-years of exposure to the IP.

AEs and lab marked abnormalities will be summarized by subject incidence and EAIR for the Placebo-controlled Phase (Weeks 0 to 16) and for the Apremilast-exposure Period. In addition, selected summaries for the Apremilast Extension Phase (Weeks 16 to 32) and the Observational Follow-up Phase (4 weeks) may be presented if deemed necessary.

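### With a completely missing last dose date and no Early Termination visit on file, SAP 8.3.5 sets treatment duration from an uncapped date that need not reflect dosing

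*SAP*

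**What the plan says.** SAP 8.3.5 imputes missing last dose dates in the analysis dataset for treatment duration. For a completely missing date the instruction is to "set last dose date to the minimum of (last known date in database, first non-missing Early Termination (ET) visit date". The first of those two terms is then defined: "Last known date in database is defined as maximum of (last visit date, lab, vital signs, AE start or end dates". The list goes on through concomitant medication and procedure dates, the last dose date on the treatment disposition page, and "treatment exposure start or end dates where doses were completely or partially taken, death date". Nothing limits the result by tablets dispensed or end of phase, and the follow-up visit is not excluded.

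These provisions depend on the result or bear on it:

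- **EAIR (SAP 9.6.1):** "The exposure time for a subject without the specific event is the treatment duration".
- **Exposure intervals (SAP 9.6.2.2):** a subject enters an interval's denominator when treatment duration exceeds its lower bound.
- **Treatment-emergent window (SAP 5.2.1):** "Adverse event started more than 28 days after the last dose of IP will not be considered as a treatment-emergent AE".
- **Late events (Protocol 10.1):** adverse events are recorded to 28 days after last dose, "as well as all SAEs made known to the investigator at any time following the protocol-required reporting period or after end of study".
- **Supply (Protocol Appendix E):** "30mg BID Titration and Treatment Card (28 day +5 Extra". The placebo card in Appendix G has the same configuration.
- **Visits:** Protocol 11.1 seeks the ET visit within 4 days of last intake. Protocol Table 3 places the follow-up visit 4 weeks after last dose, with a window of 2 weeks either side.

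**The concern.** When an ET visit exists it bounds the imputed date closely. When none exists, the rule reduces to the latest of many dates, most of which say nothing about whether tablets were being taken. Records of dosing (the disposition and exposure pages) are in the list, but inside a maximum, so any later record of another kind overrides them. A death date can only be an upper limit on dosing, yet here it can push the last dose later.

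The rule also sits badly with the rest of the SAP. A partially missing last dose date cannot go past the latest day that its known fields allow, whereas a completely missing one has no such limit. SAP 7.4.1 and 9.6.5 keep follow-up visit values out of the on-treatment summaries, but 8.3.5 does not. For a subject lost before Week 16, SAP 7.4.1.1 ends the phase at the last known study day, which gives no independent check.

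At stake is the exposure credited to these subjects, part of it in the randomized safety comparison. If the imputed date is reused for event classification, the status of individual late serious events or deaths is at stake too.

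**Working it through.** The SAP gives no figure for this rule, so there is nothing to reproduce. The check applies the rule to example subjects.

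**Inputs.** Card supply is 28 + 5 = 33 days (Protocol Appendix E). Each arm has 143 subjects (SAP 3.2), and the placebo-controlled phase lasts 16 × 7 = 112 days. The window is last dose + 28 days (SAP 5.2.1). Study days below are illustrative. Each subject has first dose on Day 1, receives only the Week 0 card, and has a completely missing last dose date.

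**Step 1: apply the rule.** Imputed last dose = min(last known date, first ET visit date); excess = imputed day − 33.

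| Records on file | Imputed last dose | Excess over card (days) |
|---|---|---|
| ET visit Day 37, serious event Day 150 | Day 37 | 4 |
| No ET; last record is the Day 29 visit | Day 29 | none |
| No ET; concomitant medication ends Day 90 | Day 90 | 57 |
| No ET; serious event starts Day 150 | Day 150 | 117 |
| No ET; death Day 200 | Day 200 | 167 |

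The ET visit controls the date in the first row. In the last three rows nothing does.

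**Step 2: exposure intervals for the Day 150 subject.** Thirty-three days of dosing gives 33 − 28 = 5 days in the >4 to ≤8 week interval and none later. The imputed 150 days gives 28 days in that interval, 28 in >8 to ≤12 weeks, and 150 − 84 = 66 beyond 12 weeks. The gain is 23 + 28 + 66 = 117 days, and the subject enters two denominators where no supply existed. Planned time per arm from Week 12 to 16 is 143 × 28 = 4,004 days, so this one subject adds 66 / 4,004 = 1.6% to the last interval.

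**Step 3: overall EAIR.** Planned exposure per arm is 143 × 112 / 365.25 = 43.85 subject-years. With k affected subjects, each 117 days over, the rate is multiplied by 43.85 / (43.85 + k × 117 / 365.25).

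| k (assumed) | Subject-years | Fall in rate |
|---|---|---|
| 1 | 44.17 | 0.7% |
| 3 | 44.81 | 2.1% |
| 5 | 45.45 | 3.5% |
| 7 | 46.09 | 4.9% |

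A second assumed range, over both arms: 1% to 5% of 286 subjects (3 to 14) overshooting by 28 to 90 days adds 3 × 28 = 84 to 14 × 90 = 1,260 days to 286 × 112 = 32,032, or 0.3% to 3.9%.

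**Step 4: treatment-emergent status, only if the imputed date is used for it.** For the Day 150 subject without an ET visit, the window closes on Day 150 + 28 = 178, so the event that set the date falls inside it. With last dose at Day 33 the window closes on Day 61 and the event falls outside. With the ET visit on Day 37 it closes on Day 65 and the event is again outside.

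**The case against.** The strongest reply is that the rule takes a minimum. A reader might infer that every completely missing last dose date is filled with the latest date in the database. The text does not say that. Protocol 6.2.1 calls for an end-of-treatment evaluation after withdrawal for any reason, and with an ET date on file the excess is a few days. This stands and confines the point to subjects without an ET visit. That group is foreseeable, because Protocol 11.1 can only ask for every attempt at the visit and SAP 7.4.1.1 provides for subjects lost before Week 16.

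A reader might also infer that late serious events will be counted as treatment-emergent. SAP 8.3.5 limits the imputation to treatment duration, and neither 5.2.1 nor 7.4 says the imputed date is used there, so this remains conditional. All serious events and all deaths are listed in any case (SAP 9.6.2.6 and 9.6.2.8). However, 8.3.5 is the only rule for a missing last dose date. If it does not apply, the 28-day window is undefined for these subjects.

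Three further inferences are weak:

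- **Imputed medication stop dates.** SAP 8.3.3 says "Partially missing prior/concomitant medication stop dates will be imputed by the latest possible date given the non-missing field(s) of the date", which for a year-only date is 31 December. Those values are created in the medication analysis dataset, whereas 8.3.5 refers to dates in the database. The documents do not show that they enter the maximum.
- **No data cut-off limit.** Observed dates are already bounded by the database snapshot.
- **Follow-up visit as the usual culprit.** That visit is timed from the last dose, so a site that holds it would normally know the last dose date.

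The number of affected subjects is assumed, and nothing in the documents points to a difference between arms.

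**Conclusion.** The point holds in a limited form. When the last dose date is completely missing and no ET visit date exists, following 8.3.5 exactly can credit a subject with more treatment than the tablets supplied. The error passes directly into the EAIR and exposure-interval denominators. For one subject it can be large (150 days against a 33-day card). For an arm it is small: 0.7% with one such subject and 4.9% with seven, on assumed counts, an assumed 117-day excess and full planned exposure otherwise. Affected subjects are probably few.

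The treatment-emergent consequence is a gap in the SAP rather than a demonstrated misclassification. It matters because a single late serious event or death is visible in an arm of 143. The efficacy analyses and the sample size are not affected.

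**What to change.** In SAP 8.3.5, for a completely missing last dose date:

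1. Treat three dates as upper caps: the first ET visit date, the last dispensing date plus days of tablets supplied minus 1, and the death date. Set last dose to the earliest cap available. In the example this gives Day 1 + 33 − 1 = Day 33.
2. Do not put the last on-treatment contact into that minimum. For a subject who takes the first card and never returns it would be Day 1, which would discard up to 32 of 33 possible days.
3. If the last known date is kept as a fallback for this case, leave out follow-up visit, adverse event, and concomitant medication or procedure dates. The partial-date rule already has its own limit and can stay.
4. State whether the imputed date also governs treatment-emergent classification in 5.2.1 and 7.4, and whether a completer's Visit 10 counts as an ET visit date.
5. Because the supply cap is calculated rather than observed, do not let it run past the data cut-off at the Week 16 analysis. SAP 7.4.2 already uses the cut-off for ongoing subjects.

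The cost is a few sentences and a small derivation change before Week 16 unblinding, using dispensing records that the trial already collects. Exposure will be slightly over-counted for a subject who stopped before the supply ran out, and slightly under-counted for one who made it last longer.
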